### **14.2.3. 12-lead ECG**

Detailed listing will be provided with all available data at each time point. Abnormal values will be marked by bolding, based on the normality ranges, provided by BMS. Normality range is 60-100 beat/minutes for heart rate, 120-200 ms for PR,  $\leq 110$  ms for QRS. For males the normal value for QTcF is between 360 and 450 ms, while for females 360 and 470 ms.

The mean of the ECG assessments will be calculated from the triplicates. The time-matched and predose changes from baseline will be calculated as follows:

**Protocol code:** D-FR-10380-002

**Protocol Title:** A phase IIA, open-label, single-arm, two stage, multi-centre study to investigate the pharmacodynamics, pharmacokinetics, safety and tolerability of repeated subcutaneous administration of BIM23B065 in subjects with acromegaly

- Time-matched changes: The time-matched mean replicated measurements of the Day-1 will be used as baseline.
- Predose changes: the mean of the triplicates of the pre-dose measurements (time point -1hour) on Day 1 will be used as baseline.

Descriptive summaries will be presented for the each ECG parameter on the mean replicated values and the changes from baseline (time-matched and predose) of RR interval, PR/PQ interval, QRS interval, QT interval, QTc interval (calculated according to the Fridericia method), and HR at each visit and time point.

A listing will be prepared for the interpretation of the ECG measurements recorded on the eCRF by visits and time points.

Subjects with clinically significant findings will be listed additionally along with the critical ECG parameter.

Number and proportion of subjects with absolute QTc values above 460, 480 and 500 msec and subjects with a QTc change more than 30 and 60 msec from baseline will be presented at each time point.

#### **14.2.4. 3-lead Holter**

All provided data (the start and stop time of the assessments, the recorded electrocardiographic measurements (ventricular rate, number of single VE beats, number of paired VE beats, number of VE runs of 3+ beats, total number of VE beats, number of single SVE beats, number of paired SVE beats, number of SVE runs of 3+ beats, total number of SVE beats, pauses (total pauses > 2 seconds) atrial fibrillation – Atrial Flutter, Second degree AV-block, Third degree AV-block), interpretation of clinical significance provided by the investigator) will be listed by patients and visit days. The interpretation will be summarized and presented in frequency tables by visit days, and in a shift table to present the change from baseline.

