### **5.2.4. Safety Endpoints and Evaluations**

- Adverse Events.
- Vital signs (supine and standing BP and HR).
- 12-lead ECG and ECG monitoring by 3-lead Holter device at specific timepoints, QTc interval will be calculated using Fridericia methodology.
- Clinical laboratory assessments: haematology, coagulation, clinical biochemistry including glucose, glucagon and insulin measurements, urinalysis.
- Putative antibodies to BIM23B065.
- Endocrine parameters: Adrenocorticotrophic Hormone (ACTH), Cortisol, Luteinizing Hormone (LH), Follicle Stimulating Hormone (FSH), Free Thyroxine (FT4), Thyroid Stimulating Hormone (TSH) and Testosterone (for males only), .
- Gallbladder echography.

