## 6. STUDY METHODS

### 6.1. Overall Study Design and Plan

This is an open-label, non-randomised, multi-centre, adaptive two-stage phase II study.

During Stage 1, up to 12 subjects will be enrolled to receive BIM23B065 BID for two weeks. The primary endpoint will be the proportion of subjects with GH  $\leq 2.5$   $\mu\text{g/l}$  or  $>50\%$  reduction from baseline GH on Day 14. The mean serum concentration of GH collected over 6 hours will be used for the baseline (Day -1) and endpoint (Day 14) GH determination.

Several sequential analyses will occur during Stage 1. The Stage 1 arm (BID administration) may be terminated early for futility during each of these interim analyses if the responder rate does not exceed the pre-determined minimum efficacy criteria. In that case, a Stage 2 arm will be initiated during which up to 12 subjects will be recruited to receive BIM23B065 three times a day (TID) for 14 days. The same sequential analysis and early termination rule for futility will apply during Stage 2 as for Stage 1.

Any subjects who withdraw prior to the Day 14 end of treatment visit may be replaced except for early withdrawal due to safety and tolerability reasons. As soon as 12 subjects (out of which at least 8 are Octreotide responders as tested during the screening period) reach Visit 8, withdrawn subjects will not be replaced.

Both the BID and TID regimen parts will consist of 3 periods (See Figure 1):

- A screening period of 21 days maximum during which the eligibility criteria will be assessed. An Octreotide test will be also performed at the latest 7 days prior to first IMP administration.
- A treatment period that will consist of twice or three times daily administrations of BIM23B065. This period will last for 14 days. The first 6 days will be a titration of BIM23B065 (0.4 mg/0.6 mg/0.8 mg BID or TID). Then a stable target dose (1.0 mg) of BIM23B065 will be BID or TID administered from Day 7 to Day 14.
- If during the study, a subject experiences any safety or laboratory events (for detailed description see Table 1 of the Protocol), they may have their dose reduced to the prior dose. The minimum dose allowed for the treatment period is 0.6mg BID or TID.
- If during the titration period, the subject experiences any cardiovascular events that meet the protocol determined criteria (for detailed description see Table 2 of the Protocol), they must remain on their current dose and not be dose escalated.

[figure not shown]

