### 10.2. Definition of Baseline

Most baseline assessments will be performed on Day -1 (Visit 3) with some exceptions. In case the data of the planned baseline assessment is not available, the last assessment which precedes the first administration of the IMP will be used as a baseline.

*Statistical Analysis Plan*

*SD-BS-014, version 1.0*

*Parent document: SOP-BS-005*

**Protocol code:** D-FR-10380-002

**Protocol Title:** A phase IIA, open-label, single-arm, two stage, multi-centre study to investigate the pharmacodynamics, pharmacokinetics, safety and tolerability of repeated subcutaneous administration of BIM23B065 in subjects with acromegaly

- For the GH and PRL calculations the mean serum concentration will be used as baseline, collected over 6 hours on the Day -1. The baseline IGF-1 will be measured on Day -1.
- For antibodies anti-BIM23B065 the baseline will be the serum concentration taken prior to octreotide test dose, on V2.
- For other laboratory assessments (all endocrine and clinical laboratory assessments, parameters of glucose metabolism etc.) baseline will be the measurement of Day -1. At the parameters of glucose metabolism more baseline values will be used in accordance to the fasting condition or the relative time from meals (the fasting condition on Day -1 will be compared with the fasting condition of the studied day, while the assessment one hour after meal will be compared to the baseline (Day -1) one hour after meal measurement etc.).
- For BP and HR, orthostatic hypotonia, and ECG, the baseline will be the corresponding measurements on Day -1 at the same time points (i.e. time-matched). For Holter the baseline will be the assessment on Day -1.
- For gallbladder echography, the baseline will be the assessment during the screening period.
- For other results of the physical examination (body weight, body temperature etc.) the D-1 assessments will be the baseline.

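### Holter results are tabulated only through the open-label investigator's interpretation; recorded rhythm and conduction findings are listed but counted by type in no table

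*SAP*

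**What the plan says.** Section 5.2.4 names Holter among the safety endpoints: "12-lead ECG and ECG monitoring by 3-lead Holter device at specific timepoints". Section 10.2 fixes its reference point: "For Holter the baseline will be the assessment on Day -1".

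Section 14.2.4 sets out the reporting. The recorded items include "number of VE runs of 3+ beats, total number of VE beats" and "pauses (total pauses > 2 seconds) atrial fibrillation – Atrial Flutter, Second degree AV-block, Third degree AV-block". These, with the recording start and stop times and the "interpretation of clinical significance provided by the investigator) will be listed by patients and visit days", go to a listing. One sentence then defines the tables: "The interpretation will be summarized and presented in frequency tables by visit days, and in a shift table to present the change from baseline". No recorded measurement is assigned to a table.

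Section 6.1 describes the setting: "This is an open-label, non-randomised, multi-centre, adaptive two-stage phase II study".

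**The concern.** For a named safety endpoint, the tables rest entirely on a judgement made with knowledge of treatment. They do not report what the device recorded. A reader of the summary tables could not learn how many subjects had AV block, a pause, atrial fibrillation or a run of ectopic beats, or how many of these were new after dosing. Findings judged significant are affected too, because the table gives a level of significance and not the kind of finding.

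The plan gives cardiovascular safety weight elsewhere. Correlating exposure with blood pressure and heart rate is a secondary objective (5.1.2), cardiovascular events during titration affect dose escalation (6.1), and blood pressure and 12-lead ECG are reported monthly (7.3). A Holter summary that does not identify findings by type fits poorly with that emphasis.

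**Working it through.** This is mainly a check of the text.

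**1. What is recorded and what is tabulated (14.2.4).**

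| Item | Number | Assigned to a table |
|---|---|---|
| Ventricular rate | 1 | no |
| Ventricular ectopic counts (single, paired, runs of 3+, total) | 4 | no |
| Supraventricular ectopic counts (same four) | 4 | no |
| Pauses > 2 s | 1 | no |
| Atrial fibrillation/flutter | 1 | no |
| Second-degree AV block | 1 | no |
| Third-degree AV block | 1 | no |
| Investigator's interpretation | – | yes: frequency and shift |

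Recorded measurements: 1 + 4 + 4 + 1 + 1 + 1 + 1 = 13, of which 0 are tabulated.

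**2. Could another section carry them?**
- 14.2.3 (12-lead ECG) covers intervals, heart rate and QTc thresholds from a different recording.
- 7.3 (monthly report) covers blood pressure and 12-lead ECG only.
- 14.1.4 (AE tables) covers only events reported as treatment-emergent AEs, which is less likely for a finding judged not significant.
- 7.4 promises summary tables in general terms and names no Holter variable.
- 7.1 leaves the review committee's outputs to a charter that is not shown.

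**3. How neighbouring assessments are handled.**
- 14.2.1: descriptive statistics on measured blood pressure and heart rate, with change from baseline.
- 14.2.2: orthostatic hypotension counted by numeric criteria.
- 14.2.3: measured values summarised and thresholds counted, for example "Number and proportion of subjects with absolute QTc values above 460, 480 and 500 msec". The ECG interpretation is only listed.
- 14.3.1: laboratory values summarised whatever relevance the investigator assigns.
- 14.4: lithiasis and sludge counted as findings.

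For the 12-lead ECG, measurements are tabulated and the interpretation is listed. For Holter it is the reverse.

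**4. What the tables would show for a new AV block judged not significant.** The scale is undefined, so there are two cases.
- Two levels (significant, not significant): the recording falls in the same cell as a normal one, and the shift table shows no change.
- Three levels (normal, abnormal not significant, abnormal significant): the subject moves from normal to abnormal, without the type of finding. If the Day -1 recording was already abnormal not significant for another reason, there is again no shift.

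In neither case is the finding identified.

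**5. Scale of one event (illustration).** Section 8 plans 12 evaluable subjects per stage. One subject is 1/12 = 8.3%. The one-sided 95% Clopper-Pearson upper limit solves (1 − p)^12 + 12p(1 − p)^11 = 0.05. At p = 0.339 the left side is 0.0070 + 0.0428 = 0.0498, so the limit is about 34%. Safety is analysed in the ITT set (section 14), which may exceed 12 through withdrawals and replacements, or fall short if a stage stops at 6 or 8.

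**The case against.** The strongest reply is that nothing is lost. Every measurement is listed by patient and visit day beside the interpretation, and with at most 24 evaluable subjects a reader can count the cases by hand. Section 3.3 allows further exploratory analyses, and section 10.7 allows further derived variables without amendment. There is no control arm, so open-label reading biases no between-arm comparison. This stands, and it keeps the point small. It does not give the endpoint a pre-specified summary by type of finding, and it does not make the change from Day -1 independent of a judgement made with knowledge of treatment.

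Two stronger readings are tempting, and the SAP supports neither.
- A reader might infer that findings judged not significant vanish from the tables altogether. That requires a scale with no level for abnormal but not significant. The SAP does not define the scale, and the CRF module plan it cites in section 4 is not shown. If such a level exists, these recordings are counted, without their type.
- A reader might infer that unequal recording lengths distort the ectopic-beat results. No summary or comparison of the counts is planned, so none can be distorted, and nothing in the document shows that recording lengths differ. Recording length matters only if such a summary is added.

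**Conclusion.** The point holds as a reporting gap in a named safety endpoint. All 13 recorded Holter measurements are listed, none is tabulated, and the only tables depend on an unblinded judgement on an undefined scale. Whether a new finding judged not significant shows as abnormal without its type, or does not show as a finding at all, turns on that scale and cannot be settled from the SAP.

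The weight is low: a desirable improvement. The primary analysis, the futility rules and the listing are unaffected. The 34% limit shows how little a single event in 12 subjects excludes. It does not measure harm from this reporting choice. The conclusion assumes that no unseen document, such as the review committee charter, already specifies Holter tables by finding for the study report.

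**What to change.** In section 14.2.4:
- Add a table, by regimen and visit day in the ITT/safety set, of the number and percentage of subjects with each recorded finding whatever the interpretation: atrial fibrillation/flutter, second-degree AV block, third-degree AV block, pauses > 2 s, ventricular runs of 3+ beats, and supraventricular runs of 3+ beats. Split each into present on Day -1 and new after dosing.
- State the categories of the interpretation scale, and keep the interpretation frequency and shift tables as secondary.
- If ventricular and supraventricular beat counts are also summarised, express them per recorded hour from the collected start and stop times, with change from Day -1.

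The cost is one or two extra tables from data already in the database. The Day -1 baseline is already defined in 10.2, and no data collection or clinical rule changes.

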### **14.3. Clinical Laboratory Assessments**

#### **14.3.1. Haematology, Clinical Chemistry, Coagulation, Urinalysis**

By patient lists will be provided with all measurements along with the unit, normal range, any deviation from it (High/Low/Abnormal values), and the relevance of being outside the normal range, identified by the investigator. Measurement results will only be presented in standard units.

**Protocol code:** D-FR-10380-002

**Protocol Title:** A phase IIA, open-label, single-arm, two stage, multi-centre study to investigate the pharmacodynamics, pharmacokinetics, safety and tolerability of repeated subcutaneous administration of BIM23B065 in subjects with acromegaly

Descriptive summaries will be presented for continuous clinical laboratory values. Categorical laboratory parameters will be summarized in frequency tables.

Laboratory measurements of patients with clinically significant abnormalities will be listed separately.

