#### **14.3.4. Endocrine Parameters**

By patient lists will be provided with all measurements along with the unit, normal range, any deviation from it, and the relevance of being outside the normal range, identified by the investigator.

Descriptive summaries will be presented from the measured values and from the calculated change from baseline (Day -1).

**Protocol code:** D-FR-10380-002

**Protocol Title:** A phase IIA, open-label, single-arm, two stage, multi-centre study to investigate the pharmacodynamics, pharmacokinetics, safety and tolerability of repeated subcutaneous administration of BIM23B065 in subjects with acromegaly

Additional list will be created of patients with clinically significant abnormal values along with the abnormal parameter.

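### SAP 14.3.1 tabulates routine laboratory values only, so for most of these tests the Day -1 baseline set in 10.2 feeds no change-from-baseline or newly-abnormal table

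*SAP*

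**What the plan says.** Section 5.2.4 of the SAP names these tests as a safety endpoint: "Clinical laboratory assessments: haematology, coagulation, clinical biochemistry including glucose, glucagon and insulin measurements, urinalysis". Section 10.2 gives them a baseline: "For other laboratory assessments (all endocrine and clinical laboratory assessments, parameters of glucose metabolism etc.) baseline will be the measurement of Day -1".

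Section 14.3.1 then plans four outputs for the routine tests:

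- By-patient listings of all measurements with normal ranges, showing "any deviation from it (High/Low/Abnormal values), and the relevance of being outside the normal range, identified by the investigator".
- Two kinds of table, one for continuous tests and one for tests reported in categories: "Descriptive summaries will be presented for continuous clinical laboratory values. Categorical laboratory parameters will be summarized in frequency tables".
- A further listing: "Laboratory measurements of patients with clinically significant abnormalities will be listed separately".

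The endocrine section, 14.3.4, is worded differently. There the summaries cover both the values and the change: "Descriptive summaries will be presented from the measured values and from the calculated change from baseline (Day -1").

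**The concern.** A baseline is defined for the routine tests, but no table planned for them uses it. The trial is open-label and has no control group, so a subject's own Day -1 value is the only reference for judging a laboratory effect.

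A summary of values by visit compares groups that may differ. Section 10.1 (Methods for Missing Data) uses observed cases and does not replace subjects who withdraw for safety or tolerability, so a visit mean can move because subjects left as well as because values changed. A paired change compares each remaining subject with himself or herself.

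Nor does any table separate a subject who was out of range before dosing from one who became so on treatment. What is at stake is how clearly the study report presents a named safety endpoint.

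**Working it through.** The SAP states no figure to reproduce here. The check sets the safety output sections side by side and asks which tables use the baseline.

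| SAP section | Parameters | Change from baseline | Shift table or subject count |
|---|---|---|---|
| 14.2.1 | Blood pressure, heart rate | Yes, time-matched | No |
| 14.2.2 | Orthostatic hypotension | No | Subject count |
| 14.2.3 | 12-lead ECG | Yes, time-matched and pre-dose | Count above QTc thresholds |
| 14.2.4 | Holter interpretation | Through the shift table | Shift table |
| 14.3.1 | Haematology, chemistry, coagulation, urinalysis | **No** | **No** |
| 14.3.2 | HbA1c, insulin, glucagon, glucose | Yes | No |
| 14.3.3 | Antibodies | No | Subject count |
| 14.3.4 | Endocrine parameters | Yes | No |

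Step 1. Is the change implied by the word values in 14.3.1? The endocrine wording in 14.3.4 names measured values and change as two separate things. The natural reading is that 14.3.1, which names only values, does not include change.

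Step 2. Does another section supply it? Section 10.7 gives a general percent-change formula but does not say which parameters receive it. Section 7.3 covers only blood pressure, heart rate and ECG. Neither commits to an output for the routine tests.

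Step 3. Could the frequency tables count newly abnormal subjects? Categorical parameters most naturally means tests reported as categories, such as urinalysis results. Even if the High/Low flags were included, a table by visit gives only marginal counts. With *a* of *n* subjects abnormal on Day -1 and *b* of the same *n* abnormal later, the newly abnormal number between max(0, *b* − *a*) and min(*b*, *n* − *a*). A shift table removes that ambiguity.

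Step 4. Which tests are affected? Section 5.2.4 counts glucose, insulin and glucagon as biochemistry, and 14.3.2 gives them change from baseline. What remains is haematology, coagulation, urinalysis and the other chemistry tests.

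Step 5. Scale. Section 8 allows 12 evaluable subjects per stage, so one subject is 1/12 = 8.3%. If a stage stops at the first interim look in section 7.2, with 6 evaluable subjects, one subject is 1/6 = 16.7%. The safety population may be somewhat larger, because some withdrawn subjects are replaced. These figures show only how much one subject weighs. The SAP gives no expected rate of laboratory abnormality or dropout from which to size an effect.

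**The case against.** The strongest reply is that nothing is lost. Every measurement is listed with its normal range and flag, Day -1 included, and with so few subjects per stage a reader can see who was abnormal before dosing and who became so. The flags rest on normal ranges and do not depend on the investigator's opinion. This stands, and it limits the point to summary tables. It does not remove it, because the SAP did not settle for listings alone for ECG, Holter or endocrine data in the same subjects.

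A second reply is that section 10.7 expects further derived variables and lets them be added without amending the SAP. That is true of derivations, but it does not commit anyone to a table. Section 3.3 says analyses not identified in the SAP will be marked as such in the study report, so it is better to name these now.

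A third reply is that treatment lasts only 14 days and no dropout rate is given, so distortion from withdrawals may be small. That also stands. The dropout argument is a reason in principle, without a demonstrated size.

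A reader might infer three stronger things that the SAP does not support:

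- That new abnormalities cannot be identified at all. The listings identify them.
- That all chemistry lacks change from baseline, or that the Day -1 definition is unused altogether. Sections 14.3.2 and 14.3.4 both use it.
- That laboratory safety goes unreviewed during the trial. Section 7.1 leaves the committee's data to its charter, which is not at hand.

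**Conclusion.** The gap is real but narrow. For haematology, coagulation, urinalysis and the chemistry tests outside 14.3.2, a baseline is defined and no planned table uses it for change or for newly abnormal subjects. The wording of the neighbouring sections suggests an omission, since change from baseline is spelled out where it is wanted.

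This is a low-priority improvement to safety reporting. It does not touch the primary analysis, the futility rules or the rule on dose-limiting toxicities. The conclusion rests on reading 14.3.1 as written, and on the assumption that no table shells outside the SAP already add these outputs.

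**What to change.** In section 14.3.1 add, by regimen (BID and TID) on the safety population:

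1. For continuous tests, descriptive summaries of change from the Day -1 baseline at each scheduled visit.
2. A shift table of baseline category (low/normal/high, or normal/abnormal) against post-dose category, with the number and percentage of subjects newly abnormal. State which post-dose value defines the category, and use the section 10.2 fallback where Day -1 is missing.

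The cost is a few sentences in the SAP and a few extra standard tables. The baseline values and range flags are already planned for the listings, so no new data are needed.

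Do not carry a single shift from Day -1 to the worst post-dose value over to 14.3.2. Insulin, glucagon and glucose there have several Day -1 baselines matched to fasting and meal timing, and one worst-value comparison would undo that matching. Section 14.3.4 already summarises change and needs no edit.
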